### **Blood samplings:**

The blood samplings including the determination of lipid parameters (ie, total-C, LDL-C, HDL-C, TG, non-HDL-C, FPG and HbA1C) should be performed in the morning, in fasting condition (ie, overnight, at least 10 to 12 hours fast and refrain from smoking), and before IMP injection for all site visits throughout the study. Alcohol consumption within 48 hours and intense physical exercise within 24 hours preceding the blood sampling are discouraged.

*Note: if the patient is not in fasting conditions, the blood sample will not be collected and a new appointment will be given the day after (or as close as possible to this date) to the patient with instruction to be fasted (see above conditions) and not having taken IMP (injection to be delayed accordingly).*

In case the lipid results are made available during the visit, the lipid results performed at local laboratory will be reviewed at the on-site visit by the investigator, and, in case a dose adjustment is required, the dose will be modified immediately or the patient will be requested to come to the site within a few days for an unscheduled visit, so that the dose can be adjusted as needed.

The unscheduled dispensation visit will be similar to the “dispensation only” visits, eg, V10/W36.

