### 2.1.3 Efficacy endpoints

Efficacy endpoints include lipid parameters: calculated LDL-C, Total-C, HDL-C, TG, non-HDL-C. Total-C, HDL-C, TG will be provided by a local Laboratory. LDL-C will be calculated using the Friedewald formula [\(1\)](#) at all site visits (see [Section 2.5.1](#)). One of the most important limitations of the Friedewald formula is that it is not appropriate at TG concentrations >400 mg/dL, anyway and in order to simplify the computations this formula will be used regardless of the TG values. Non-HDL-C is calculated by subtracting HDL-C from the Total-C.

Unless otherwise specified, all lipid values (scheduled or unscheduled, fasting or not fasting) may be used to provide a value for the efficacy endpoints. All measurements, scheduled or unscheduled, fasting or not fasting, will be assigned to analysis windows defined in [Table 2](#) in order to provide an assessment from Week 4 to the end of the study.

The main efficacy endpoint will be the LDL-C at Week 12 (change from baseline). Nevertheless, all efficacy endpoints will be described at each time point.

For all post-baseline time points, the value used for the analyses at a given time point will be the value obtained within the corresponding analysis window. The baseline value is defined as the last available measurement obtained before the date of the first injection of alirocumab.

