#### **2.4.5 Analyses of safety data**

##### *General common rules*

All safety analyses will be performed on the Safety population using the following common rules:

- The baseline value will be defined as the last available value before the first alirocumab injection.
- The potentially clinically significant abnormality (PCSA) values are defined as abnormal values considered medically important by the Sponsor according to predefined criteria/thresholds based on literature review and defined by the Sponsor for clinical laboratory tests and vital signs (PCSA version dated May 2014, see [Appendix A](#)).
- PCSA criteria will determine which patients had at least 1 PCSA during the TEAE period, taking into account all evaluations performed during the TEAE period, including unscheduled or repeated evaluations. The number of all such patients will be the numerator for the PCSA percentages.

- The treatment-emergent PCSA denominator for a given parameter will be based on the number of patients assessed for that given parameter in the TEAE on the safety population.
- The worst on-treatment value is defined as the nadir and/or the peak value during the treatment period according to the direction (Min or Max) of the abnormality as defined the PCSA list. The last on-treatment value is defined as the last value collected during the treatment period.
- All measurements, scheduled or unscheduled, fasting or not fasting, will be assigned to analysis windows defined in [Section 2.5.4](#) in order to provide an assessment for all time points.

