#### **2.4.5.3 Analyses of laboratory variables**

The summary statistics (including mean, median, Q1, Q3, SE Min and Max) of some laboratory variables (absolute values and changes from baseline) will be calculated for each visit, last and worst value assessed during the treatment period. Since no central laboratory was used in this study, results obtained from local laboratories will be converted into the units listed in [Appendix A](#). For a given parameter, if no unit is indicated, no quantitative analysis will be performed.

The incidence of PCSA (list provided in [Appendix A](#)) at any time during the TEAE period will be summarized by biological function whatever the baseline level and/or according to the following baseline status categories:

- Normal/missing.
- Abnormal according to PCSA criterion or criteria.

For parameters for which no PCSA criteria are defined, similar table(s) using the normal range will be provided. A listing of patients with at least one post-baseline PCSA will be provided.

The absolute change in HbA1c (%) will be assessed from baseline to Weeks 12, 24, 48, 72, 96 and EOT/EOS.

For parameters HbA1c, FPG and LDL-C plots will be displayed; mean changes from baseline with the corresponding SE will be plotted over time (at same time points).

For the parameters assessed through dipstick urinalysis, no central laboratory was used. As a consequence, the results of statistical analyses on these parameters will have to be interpreted with caution.

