**Table 3 - Analysis windows definition**

Time point	Targeted study day	Analysis window in study days
Week 4	29	15 to 42
Week 8	57	43 to 70
Week 12	85	71 to 98
Week 24	169	155 to 182
Week 36	253	239 to 266
Week 48	337	316 to 357
Week 60	421	400 to 441
Week 72	505	484 to 525
Week 84	589	568 to 609
Week 96	673	652 to 693
Week 108	757	736 to 777
Week 120	841	820 to 861
Follow-up a	Last injection + 10 weeks	Last injection + 10 weeks ± 4 weeks

Study days are calculated from the day of first injection, the day of first injection being Day 1.

a For the patients who participated in the study according to the initial protocol and who prematurely discontinued the treatment irrespective of the reason and those who will switch to another LMT

If multiple valid values of a variable exist within a time window, the nearest from the targeted study day will be selected. If the difference is a tie, the value after the targeted study day will be used. If multiple valid values of a variable exist within a same day, then the first value of the day will be selected.

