Creatinine	≥150 µmol/L (Adults) ≥30% change from baseline ≥100% change from baseline	Benichou C, 1994.
Uric Acid		
Hyperuricemia	>408 µmol/L	Harrison - Principles of internal Medicine 17 th Ed. 2008.
Hypouricemia	<120 µmol/L	
Blood Urea Nitrogen	≥17 mmol/L	
Chloride	<80 mmol/L ≥115 mmol/L	
Sodium	≤129 mmol/L ≥160 mmol/L	
Potassium	<3 mmol/L ≥5.5 mmol/L	FDA Feb 2005.
Total Cholesterol	≥7.74 mmol/L	Threshold for therapeutic intervention.
Triglycerides	≥4.6 mmol/L	Threshold for therapeutic intervention.
Lipasemia	≥3 ULN	
Amylasemia	≥3 ULN	
Glucose		
Hypoglycaemia	≤3.9 mmol/L and <LLN	ADA May 2005.
Hyperglycaemia	≥11.1 mmol/L (unfasted); ≥7 mmol/L (fasted)	ADA Jan 2008.
HbA1c	>8%	
Albumin	≤25 g/L	
CRP	>2 ULN or >10 mg/L (if ULN not provided)	FDA Sept 2005.
Hematology		
WBC	<3.0 Giga/L (Non-Black); <2.0 Giga/L (Black) ≥16.0 Giga/L	Increase in WBC: not relevant. To be interpreted only if no differential count available.
Lymphocytes	>4.0 Giga/L	

[figure not shown]
Parameter	PCSA	Comments
Neutrophils	<1.5 Giga/L (Non-Black); <1.0 Giga/L (Black)	International Consensus meeting on drug-induced blood cytopenias, 1991. FDA criteria.
Monocytes	>0.7 Giga/L or >ULN (if ULN $\geq$ 0.7 Giga/L)	
Basophils	>0.1 Giga/L	
Eosinophils	>0.5 Giga/L or >ULN (if ULN $\geq$ 0.5 Giga/L)	Harrison- Principles of internal Medicine 17 th Ed. 2008.
Hemoglobin	$\leq$ 115 g/L (Male); $\leq$ 95 g/L (Female) $\geq$ 185 g/L (Male); $\geq$ 165 g/L (Female) Decrease from Baseline $\geq$ 20 g/L	Criteria based upon decrease from baseline are more relevant than based on absolute value. Other categories for decrease from baseline can be used ( $\geq$ 30 g/L, $\geq$ 40 g/L, $\geq$ 50 g/L).
Hematocrit	$\leq$ 0.37 v/v (Male) ; $\leq$ 0.32 v/v (Female) $\geq$ 0.55 v/v (Male) ; $\geq$ 0.5 v/v (Female)	
RBC	$\geq$ 6 Tera/L	Unless specifically required for particular drug development, the analysis is redundant with that of Hb. Otherwise, consider FDA criteria.
Platelets	<100 Giga/L $\geq$ 700 Giga/L	International Consensus meeting on drug-induced blood cytopenias, 1991.
Urinalysis		
pH	$\leq$ 4.6 $\geq$ 8	
Vital signs		
HR	$\leq$ 50 bpm and decrease from baseline $\geq$ 20 bpm $\geq$ 120 bpm and increase from baseline $\geq$ 20 bpm	To be applied for all positions (including missing) except STANDING.

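### Against the protocol's fasting rule, the SAP admits non-fasting values to by-visit glucose and lipid summaries and lets them displace fasting ones; this can bias FPG, TG and calculated LDL-C

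*SAP*

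**What the plan says.** **Protocol.** Section 10 (Blood samplings) covers the lipid panel, FPG and HbA1c at all site visits. Sampling "should be performed in the morning, in fasting condition (ie, overnight, at least 10 to 12 hours fast and refrain from smoking". For an unfasted patient the same section states that "if the patient is not in fasting conditions, the blood sample will not be collected and a new appointment will be given the day after"; some leeway on that date is allowed. Section 10 (Other assessments), which lists HbA1c and serum glucose, only expresses a preference for fasting. Footnotes to the flow chart in Section 1.2 let a laboratory result up to one week old stand in for the lipid and chemistry panels and state no fasting condition.

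**SAP.** For efficacy, Section 2.1.3 says that "all lipid values (scheduled or unscheduled, fasting or not fasting) may be used to provide a value for the efficacy endpoints". For safety, Section 2.4.5 says: "All measurements, scheduled or unscheduled, fasting or not fasting, will be assigned to analysis windows". When a window in Section 2.5.4 holds several values, "the nearest from the targeted study day will be selected"; a tie goes to the later day, and within a day the first value counts. Baseline is the last available value before the first injection, again without a fasting condition. Section 2.1.4.3 names fasting plasma glucose as a chemistry variable, and under Section 2.4.5.3 "For parameters HbA1c, FPG and LDL-C plots will be displayed", as mean change over time. LDL-C is calculated by the Friedewald formula at any TG level (Sections 2.1.3 and 2.5.1).

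Fasting state otherwise matters only in the hyperglycaemia limits of Appendix A: "≥11.1 mmol/L (unfasted); ≥7 mmol/L (fasted"). Section 1.5 does not mention non-fasting values among the changes from the protocol, Section 1.6 reports no modifications, and no fasting-only sensitivity analysis is planned.

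**The concern.** The protocol sets a sampling condition and the analysis then ignores it. Protocol 11.4.3 provides for scheduled and unscheduled measurements; the extension to non-fasting ones appears only in the SAP.

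This goes beyond filling gaps. Because the selection rule is blind to fasting state, a compliant fasting sample can be dropped in favour of a non-fasting one.

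Three outputs are exposed:
- by-visit means and plots of a variable that the SAP itself calls fasting glucose, within the primary safety analysis;
- percent change in TG, a key secondary endpoint;
- calculated LDL-C, the main efficacy endpoint, with the <70 and <100 mg/dL proportions and the counts of very low LDL-C in SAP 2.4.4.4.

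The study has one arm, so no control group would offset an error.

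**Working it through.** The plan gives no figure on this point to reproduce. The check has two parts.

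**1. Selection rule (SAP 2.5.4), Week 12 target Day 85**

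| Values in the window | Deciding rule | Value used |
|---|---|---|
| Fasting Day 82, non-fasting Day 85 | nearest (3 v 0 days) | non-fasting |
| Non-fasting Day 85, fasting Day 86 | nearest (0 v 1 day) | non-fasting |
| Fasting Day 84, non-fasting Day 86 | tie, later day | non-fasting |
| Both on Day 85, non-fasting drawn first | first of the day | non-fasting |

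The second row is the pair that arises if a site draws blood from an unfasted patient by mistake and then rebooks for the next day as the protocol asks.

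**2. Size, under stated assumptions**

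From the SAP: LDL-C = Total-C - HDL-C - TG/5 (mg/dL). Assumed, because the documents give no figures: TG rise d = 30 to 100 mg/dL with Total-C and HDL-C unchanged; glucose rise g = 1 to 3 mmol/L; true LDL-C 160 falling to 80 mg/dL; true TG 150 falling to 135 mg/dL; non-fasting share f0 at baseline and f12 at Week 12.

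*One affected value.* Calculated LDL-C falls by d/5: 30/5 = 6, 50/5 = 10, 100/5 = 20 mg/dL. At a baseline of 160 mg/dL that is 6/160 = 3.75, 10/160 = 6.25 and 20/160 = 12.5 percentage points. For the 70 mg/dL target, d = 50 reclassifies true values from 70 to just under 80, and d = 100 those from 70 to just under 90. A true 85 drops below 70 only if d exceeds (85 - 70) x 5 = 75.

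*Non-fasting values at Week 12 only (f0 = 0).* Shift in mean percent change: LDL-C = -100 x f12 x (d/5)/160; TG = +100 x f12 x d/150. Shift in mean FPG = f12 x g.

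| f12 | LDL-C, points | TG, points | FPG, mmol/L |
|---|---|---|---|
| 2% | -0.075 to -0.25 | +0.4 to +1.33 | +0.02 to +0.06 |
| 5% | -0.19 to -0.63 | +1.0 to +3.33 | +0.05 to +0.15 |
| 20% | -0.75 to -2.5 | +4.0 to +13.3 | +0.20 to +0.60 |

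*Equal shares at both times.* The mean ratio of Week 12 to baseline is (80 - f x d/5) x [(1 - f)/160 + f/(160 - d/5)] for LDL-C, and correspondingly for TG with +d. With f = 10% and d = 30: 79.4 x 0.006274 = 0.4982, a shift of -0.18 points. With f = 20% and d = 100: 76 x 0.006429 = 0.4886, a shift of -1.14 points. TG shifts by +0.47 and +5.07 points.

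*Baseline only (f0 = 10%).* LDL-C: 0.10 x (80/154 - 80/160) = +0.19 points at d = 30, and 0.10 x (80/140 - 80/160) = +0.71 at d = 100. TG: 0.10 x (135/180 - 135/150) = -1.5 points, and 0.10 x (135/250 - 135/150) = -3.6. The signs reverse.

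**The case against.** The strongest reply is that few such values should exist. The protocol stops them at source, and the screening visit in Section 10.1.1 again asks for a fasting sample. No protocol procedure routinely yields a second lipid panel near Week 12. A titration visit is modelled on dispensation visits, whose list in Section 10.1.2.4 has no blood draw, and the unscheduled panel in Section 10.6.3 covers hematology, chemistry and liver tests but not lipids. With the visit due on Day 85 ±3, an on-time fasting value is displaced only by a sample within three days of target. One-week-old results seem meant for screening, since the lipid and chemistry footnotes speak of a retest before inclusion; any error from them would then sit at baseline.

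There are also safeguards. HbA1c is plotted beside FPG, glucose abnormality counts use separate fasted and unfasted limits, medians are reported, Total-C and non-HDL-C carry no TG term, and every analysis is descriptive.

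All of this stands and limits the likely size. It does not remove the mismatch between the documents or justify preferring a non-fasting value when a fasting one is available.

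Three stronger readings are tempting but unsupported:
- *The results are biased in the drug's favour.* The number and timing of non-fasting values are unknown, and the sign turns on timing.
- *The protocol flatly forbids non-fasting glucose.* Blood samplings does so for FPG, but Other assessments only prefers fasting.
- *Fasting status is certainly recorded.* Appendix A needs it, but that appendix appears to be a general sponsor list: it also covers ECG, lipase and orthostatic blood pressure, which are not in the flow chart.

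**Conclusion.** The point holds as a mismatch between protocol and SAP with a defect in the selection rule. Non-fasting values are admitted and can displace fasting ones, and the SAP does not declare this as a change. It can bias by-visit FPG and TG means and, through TG/5, calculated LDL-C and target attainment.

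The size cannot be determined from the documents. If sites follow the sampling rule, the shift in mean LDL-C is probably small: at most 2.5 points even at a 20% share and a 100 mg/dL TG rise, against reductions of 45.7% and 61.0% at Week 24 quoted in Protocol Section 4 for 150 mg Q2W. TG and FPG are more sensitive, and individual patients close to an LDL-C threshold can change category. These figures rest wholly on the assumed shares, rises and lipid levels.

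The change is worth making because it is cheap and removes an avoidable error in a single-arm study. The main conclusions are not shown to be at risk.

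**What to change.** - In SAP 2.1.3, 2.4.5 and 2.5.4, and in the baseline definition, select a fasting value first. For calculated LDL-C, use a non-fasting value only when the window (or the baseline period) holds no fasting one.
- Restrict by-visit FPG and TG summaries and plots to samples recorded as fasting.
- Report the number of non-fasting values at each time point, and show the Week 12 LDL-C results with and without them.
- Leave the counts of potentially clinically significant abnormalities as they are.
- List the handling of non-fasting values in SAP 1.5, and reconcile the two protocol statements on fasting for glucose.
- Confirm that the eCRF records fasting status. If it does not, the glucose limits in Appendix A cannot be applied as written either.

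The cost is SAP wording and, if fasting status is recorded, a simple filter. A few patients lose an FPG or TG value at a visit. The fallback for LDL-C means that the mITT population, which requires a Week 12 LDL-C value, does not shrink.

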### **2.1.3.1 Primary efficacy endpoint(s)**

No primary efficacy endpoints are defined since the primary objective is dedicated to safety.

### **2.1.3.2 Secondary efficacy endpoint(s)**

The main efficacy secondary endpoint will be:

- The percent change in calculated LDL-C from baseline to Week 12 (on-treatment estimand).

The key secondary efficacy endpoints will include:

- The proportion of patients reaching calculated LDL-C <100 mg/dL (2.59 mmol/L) at Week 12 (on-treatment estimand).
- The proportion of patients reaching calculated LDL-C <70 mg/dL (1.81 mmol/L) at Week 12 (on-treatment estimand).
- The proportion of patients with LDL-C <70 mg/dL (1.81 mmol/L) and/or ≥50% reduction from baseline in calculated LDL-C at Week 12 (on-treatment estimand).
- The percent change in non-HDL-C, total-C, HDL-C, TG from baseline to Week 12 (on-treatment estimand).

The other secondary efficacy endpoints will be:

- The proportion of patients who were up-titrated from 75 mg Q2W to 150 mg Q2W of alirocumab during the observational period based on investigator's judgment (on-treatment estimand).
- The proportion of patients who were down-titrated from 150 mg Q2W to 75 mg Q2W of alirocumab during the observational period based on investigator's judgment (on-treatment estimand).
- The reasons (ie, LDL-C threshold, AE) that triggered a down-titration or an up-titration of alirocumab (on-treatment estimand).
- The percent change in LDL-C from baseline over time, using all LDL-C values during the efficacy treatment period (on-treatment estimand) defined in [Section 2.3.1](#).
- The absolute change in calculated LDL-C (mg/dL and mmol/L) from baseline over time, using all LDL-C values during the efficacy treatment period (on-treatment estimand).
- The proportion of patients reaching calculated LDL-C <100 mg/dL (2.59 mmol/L) over time (on-treatment estimand).
- The proportion of patients reaching calculated LDL-C <70 mg/dL (1.81 mmol/L) over time (on-treatment estimand).
- The proportion of patients with calculated LDL-C <70 mg/dL (1.81 mmol/L) and / or ≥50% reduction from baseline in calculated LDL-C over time (on-treatment estimand).
- The percent change in non-HDL-C, total-C, HDL-C, TG from baseline over time (on-treatment estimand).
- The absolute change in non-HDL-C, total-C, HDL-C, TG (mg/dL and mmol/L) from baseline over time (on-treatment estimand).

Since the study duration for each participating country will depend on when alirocumab becomes commercially available and reimbursed, with a minimum duration of 12 weeks and up to a maximum of 120 weeks, the secondary efficacy endpoints associated to the lipid parameters will be also assessed at the following time points depending on countries: Weeks 4, 8, 12, 24, 48, 72, 96 and 120 (EOT/EOS).

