## 9.2 SECONDARY ENDPOINTS

### 9.2.1 Secondary efficacy endpoints

The main efficacy secondary endpoint will be:

- The percent change in calculated LDL-C from baseline to Week 12 (main timepoint).

The key secondary efficacy endpoints will include:

- The proportion of patients reaching calculated LDL-C <100 mg/dL (2.59mmol/L) at Week 12.
- The proportion of patients reaching calculated LDL-C <70 mg/dL (1.81mmol/L) at Week 12.
- Proportion of patients with LDL-C <70 mg/dL (1.81 mmol/L) and/or  $\geq 50\%$  reduction from baseline in LDL-C (if LDL- C  $\geq 70$  mg/dL [1.81 mmol/L]) at Week 12.
- The percent change from baseline to Week 12 in non-HDL-C, total-C, HDL-C, and TG levels.

Since the study duration for each participating country will depend on when alirocumab becomes commercially available and reimbursed, with a minimum duration of patient's participation of 12 weeks and up to a maximum of 30 months, the secondary efficacy endpoints listed above will also be assessed at the following time points depending on countries: Weeks 4, 8, 12, 24, 48, 72, 96, 108, and EOT/EOS.

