**10.1.2.5 End-of-treatment (EOT/EOS) visit: Visit 17 / Week 120 (Day 841 +7)**

This EOT/EOS visit should occur at least 14 days (+7 days) after last injection (ie, within a 14-21 days' time window).

This visit may occur before Week 120 if the commercial alirocumab (Praluent) becomes available before this date in a given country.

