**11.4.3 Analyses of efficacy data (see [Section 9.2.1](#))**

Efficacy variables will be explored through descriptive statistics.

Percent changes from baseline will be summarized at Weeks 4, 8, 12 and 24 and at Week 48, 72, 96, EOT/EOS in the mITT population using number of available data, mean, SD, median, minimum, and maximum. For percent changes, 95% confidence intervals of the mean will also be provided.

All measurements, scheduled or unscheduled will be assigned to analysis windows defined in the statistical analysis plan (SAP).

The proportions of patients reaching the different targets defined for LDL-C will be provided with their corresponding 95% confidence intervals.

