#### **2.5.4 Windows for time points**

Data analyzed by time point (including efficacy, laboratory safety data, vital signs) will be summarized using the analysis windows given in [Table 3](#). These analysis windows will be applicable for all analyses, and they are defined to provide more homogeneous data for time point-specific analyses.

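### The SAP ties the lipid EOT/EOS time point to Week 120 and gives it no window of its own, so exits on Days 99 to 819 cannot be summarised as EOT/EOS

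*SAP*

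**What the plan says.** **Lipid time points.** SAP 2.1.3.2 gives "the following time points depending on countries: Weeks 4, 8, 12, 24, 48, 72, 96 and 120 (EOT/EOS". Protocol 9.2.1 gives "Weeks 4, 8, 12, 24, 48, 72, 96, 108, and EOT/EOS", and Protocol 11.4.3 summarises percent changes "at Week 48, 72, 96, EOT/EOS in the mITT population". Both protocol lists keep EOT/EOS apart from any week number.

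**When EOT/EOS happens.** Protocol 10.1.2.5 places the visit 14 to 21 days after the last injection and adds: "This visit may occur before Week 120 if the commercial alirocumab (Praluent) becomes available before this date in a given country".

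**How values are assigned.** SAP 2.1.3 uses, at each post-baseline time point, the value found inside that time point's window. SAP 2.5.4 says: "These analysis windows will be applicable for all analyses". Under Table 3, "Study days are calculated from the day of first injection, the day of first injection being Day 1". The table has twelve week rows, the last being Week 120 (target Day 841, window Days 820 to 861), and no EOT/EOS row. The only row anchored on the last injection is a follow-up row, "Last injection + 10 weeks ± 4 weeks". Its footnote restricts it to initial-protocol patients who stopped early or switched to another lipid therapy.

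**HbA1c.** SAP 2.4.5.3 assesses change "from baseline to Weeks 12, 24, 48, 72, 96 and EOT/EOS", without tying EOT/EOS to Week 120.

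**The concern.** Length of treatment is set by when each country makes the product available and reimbursed, so the exit visit can fall on almost any day from about Week 12 onward. Lipids and HbA1c are sampled at that visit. For a patient who leaves early, it is the measurement that closes the period of exposure.

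If EOT/EOS means Week 120, the row labelled EOT/EOS describes only patients treated to about Week 120, that is, those in late-reimbursing countries who also stayed on treatment. A reader would take it for the study's end-of-treatment result.

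The SAP also conflicts with itself. Section 2.1.3 says every lipid measurement will be placed in a window so as to cover Week 4 to the end of the study. Section 2.1.3.2 promises LDL-C change over time from every value in the efficacy treatment period, which runs to 21 days after the last injection (SAP 2.3.1) and so takes in an on-schedule exit sample. Table 3 cannot deliver either statement for an exit that falls between its windows.

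**Working it through.** **1. Reproduce Table 3.** Target day = 7 × week + 1. For Week 120, 7 × 120 + 1 = 841, as stated. The formula returns all twelve targets.

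**2. Exits that cannot reach the EOT/EOS row.** The Week 12 window closes on Day 98 and the Week 120 window opens on Day 820. Days 99 to 819 number 819 − 99 + 1 = 721, and none of them maps to Week 120.

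**3. How much of that span has any window.**

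| Rows | Days covered |
|---|---|
| Weeks 24 and 36 | 2 × 28 = 56 |
| Weeks 48, 60, 72, 84, 96 and 108 | 6 × 42 = 252 |
| Total | 308 |

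Uncovered: 721 − 308 = 413 days, and 413/721 = 57%. Counting the gaps directly gives the same total: Days 99–154 (56), 183–238 (56), 267–315 (49), and six gaps of 42 days (358–399, 442–483, 526–567, 610–651, 694–735, 778–819); 56 + 56 + 49 + 252 = 413.

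**4. Can the follow-up row take the exit visit?** Ten weeks ± 4 weeks is 70 ± 28, or 42 to 98 days after the last injection. A visit at 14 to 21 days cannot fall there.

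**5. Share of exit values in no window.** The documents give no exit distribution, so each pattern below is an assumption.

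| Assumed exit pattern | In no window |
|---|---|
| Visit at the end of a 6-pen (12-week) kit: target day of Weeks 12, 24, …, 108, plus 0 to 7 days | 0 of 72 (0%) |
| Last injection on a 12-weekly visit day (Weeks 12 to 108), visit 14 to 21 days later | 30 of 72 (42%) |
| Last injection on any 2-weekly date from Week 10 to Week 116, visit 14 to 21 days later | 239 of 432 (55%) |
| Visit spread evenly over Days 99 to 819 | 413 of 721 (57%) |

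In the second pattern, all exits after Weeks 12, 24 and 36 fall in a gap (3 × 8 = 24), as does one of the eight allowed days after each of the six later visits (6); 24 + 6 = 30.

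An exit value on Days 99 to 819 that does fall in a window is reported, at best, under a nominal week. It may not be reported even there, because Table 3 keeps only the value nearest the target day and a scheduled sample may be nearer.

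**6. What the calendar allows.** The first patient was enrolled on 08 July 2015 (SAP 1.5), and the last visit is due no later than the beginning of 2018 (Protocol 6.2.2). Reading that as 1 January to 31 March 2018 (assumption), a patient reaches Day 820 only if first injected by about 5 October 2015 to 2 January 2016, which is 819 days earlier. Enrolment by date is not given, so no percentage follows. Later starters could not reach the Week 120 window even without a reimbursement exit.

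**7. HbA1c.** The time point is named, but Table 3 applies and has no row for it. SAP 2.4.5.3 also summarises a last value, but the definitions differ: SAP 2.4.5 takes the last value in the treatment period, while SAP 2.5.1 takes the value at or just before the last dose, which would leave out an exit sample. The abnormality (PCSA) summaries stop 14 days after the last injection, so only 1 of the 8 permitted visit days (+14 to +21) is inside them.

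**The case against.** Several points on the other side are sound.

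- The label has a source. The protocol's flow chart and visit heading also attach Week 120 to EOT/EOS, and for a patient who completes the schedule the two coincide.
- Study-day windows serve a purpose stated in SAP 2.5.4, namely homogeneous data. A row pooling exits from Week 12 to Week 120 mixes very different exposures.
- Kits hold 12 weeks of pens. If exits follow kit ends, every exit value lands in some window.
- Some lipid analyses need no window: very low LDL-C at any time, and LDL-C before discontinuation (SAP 2.4.4.4). All analyses are descriptive.

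These points limit the size of the problem. They do not give early leavers an EOT/EOS result, which the protocol lists as a time point. The pooling objection is met by showing exit week beside the row.

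A reader might infer more than the documents support:

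- *That most exit values are lost from the analysis.* The share in no window runs from 0% to 57% with the assumed exit pattern, and the window-free analyses still use the values.
- *That 79% would miss every reported lipid time point.* With evenly spread exits, 413 + 28 + 3 × 42 = 567 of 721 days lie outside Weeks 24, 48, 72 and 96. That counts Weeks 36, 60, 84 and 108 as unreported. SAP 2.1.3 describes efficacy endpoints at each time point and Table 3 gives those weeks windows, so their status is unclear.
- *That HbA1c is also fixed to Week 120.* SAP 2.4.5.3 names EOT/EOS separately. Its handling is undefined, which is a different fault.
- *That Table 3 closes too early for patients treated to the maximum.* Thirty months is 30 × 365.25/12 = 913 days (130.4 weeks), past Day 861. But SAP 2.1.3.2 states a 120-week maximum and the visit schedule ends at Day 841 + 7. This is a separate mismatch between two stated durations.

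**Conclusion.** The concern holds for lipids. Following SAP 2.1.3.2 and Table 3 as written, no lipid value from an exit on Days 99 to 819 can be summarised as EOT/EOS, and the row with that label is restricted to patients treated to about Week 120. This follows from the stated rules under any exit pattern. So does the count of 413 uncovered days out of 721 (57%). The share of patients' exit values left in no window does depend on exit timing: 0% for kit-aligned exits, about 57% for evenly spread ones.

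For HbA1c the fault is narrower: a named time point without a window. The main and key Week 12 efficacy endpoints and the adverse-event analyses are not touched.

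**What to change.** - In SAP 2.1.3.2, list Week 120 and EOT/EOS as two time points: '120, and EOT/EOS'.
- Add an EOT/EOS row to Table 3, defined by the EOT/EOS visit and anchored on the last injection (+14 to +21 days, the protocol's own visit window). Apply it to lipids and HbA1c. Every on-schedule exit sample is then assigned, whatever the exit date.
- State how the separate EOT and EOS visits of original-protocol patients (SAP 1.1) map to the row, and which sample counts for early discontinuers, who also have an unscheduled visit soon after stopping (Protocol 10.3.2.2).
- Show the distribution of exit week beside the summary.
- State whether Weeks 36, 60, 84 and 108 are reported for lipids. Protocol 9.2.1 lists Week 108; the SAP list does not. Protocol Section 10 schedules no lipid sample at these visits, so those windows would hold mainly exit and unscheduled values.
- Reconcile the two definitions of the last on-treatment value (SAP 2.4.5 and 2.5.1), and the 30-month and 120-week statements of maximum duration.

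The cost is one table row, one summary column and a few clarifying sentences, using data already collected. The small downside is that the new row pools different exposure lengths, which is why the exit-week distribution should sit beside it.
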